# C) DEFINITIONS OF TRUE POSITIVE, FALSE POSITIVE, TRUE NEGATIVE, AND FALSE NEGATIVE PATIENTS AND REGIONS

Pathology will be considered superior to imaging and clinical follow-up when available as described below. Patient and region level classification will be performed for each blinded reader, and be reported separately. The following criteria serve as a guide for interpretation. However not all findings on a lesions, region and patient level can be detailed here and investigators may deviate from these criteria in individual patients. These will be recorded for each interpretation that is not described in this protocol for the definition of a region or patient.

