# **Secondary Endpoints:**

- 1. Prognostic value of the F-DCFPyL PET/CT miTNM classification (described below) for biochemical PFS, radiographic PFS and overall survival.
- 2. Positive predictive value (PPV) on a per-patient and per-region basis (Table 1) of F-DCFPyL PET for detection of tumor location confirmed by histopathology/biopsy or follow-up assessed separately for initial staging and restaging.

Region	Description
1	Prostate Bed
2	Pelvic lymph nodes
3	Extrapelvic soft tissue, lymph nodes and visceral metastases
4	Bone metastases

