#### 1.1.9.5 Positive predictive value (PPV) on a per-patient and per-region basis Analysis:

PPVs on a per-patient and per-region-basis of F-DCFPyL PET for detection of tumor location confirmed by histopathology/biopsy, clinical and conventional imaging follow-up will be calculated and reported along with the corresponding two-sided 95% confidence intervals. The confidence intervals will be constructed using the Wilson score method. PPV will be reported for each of the three blinded readers independently.

Detection rates on a per-patient basis of  $^{18}$ F-DCFPyL PET stratified by PSA value (0.2 - <0.5, 0.5 - <1.0, 1.0 - <2.0, 2.0 - <5.0,  $\geq$ 5.0) will be summarized in tabular format and compared between PSA strata using chi-square analysis.

Detection rate is defined as number of patients with F-DCFPyL positive disease, independent of pathology, imaging or clinical follow-up. A detection rate will be reported for each reader independently stratified by PSA.

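### Investigators may depart from the true/false-positive criteria case by case, and the plan does not say which classification the reported PPV uses

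*Combined protocol and SAP*

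**What the plan says.** PPV, per patient and per region, is the second secondary endpoint (section 1.1.3.3). Whether a PET-positive finding counts as TP or FP is set out in section 1.1.8.4, part 2. Part A gives lesion criteria based on follow-up imaging and PSA, part B gives pathology rules, and part C rolls these up to regions and patients.

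Part C opens with four relevant statements:

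- Priority: "Pathology will be considered superior to imaging and clinical follow-up when available as described below".
- Status: "The following criteria serve as a guide for interpretation".
- Permission: because not every finding can be set out in advance, "investigators may deviate from these criteria in individual patients".
- Recording: "These will be recorded for each interpretation that is not described in this protocol for the definition of a region or patient".

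Part C gives no trigger, limit, adjudicator or deadline for a deviation.

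Section 1.1.9.5 says that PPVs "will be calculated and reported along with the corresponding two-sided 95% confidence intervals". It adds "The confidence intervals will be constructed using the Wilson score method" and "PPV will be reported for each of the three blinded readers independently". It does not mention deviations, a PPV restricted to the written criteria, or a count of departures.

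**The concern.** Assigning TP or FP means matching a PET-positive lesion to its later pathology, imaging or PSA course. Someone who departs from the rule at that stage will ordinarily have both in hand, and nothing in the plan states otherwise. The blinding that the plan mentions belongs to the PET readers. Follow-up imaging is read locally, and local readers are told where the blinded readers saw lesions that they had not reported themselves.

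Discretion of this kind can move a PPV, and the Wilson interval does not show it because it reflects sampling error only. If section 1.1.9.5 is silent on which classification is analysed, a reader of the results cannot tell how much of the PPV comes from the rules and how much from judgement.

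**Working it through.** **1. What the permission covers.** The status sentence points to the criteria that follow it, which are the region and patient definitions in part C. The recording sentence is also limited to the definition of a region or patient. The lesion thresholds (part A) and pathology rules (part B) come earlier. However, the sentence granting the permission also refers to findings at lesion level, so a wider reading is open.

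**2. What recording secures.** It covers interpretations that the protocol does not describe. It does not clearly cover overriding a criterion that is described, and it does not ask for the criteria-based result or the reason. A criteria-only PPV might therefore not be recoverable afterwards.

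**3. Whether uncovered cases already have a rule.** Largely, yes. The lymph node, visceral, bone and prostate subsections of part A each class cases that meet neither TP nor FP criteria as unevaluable. Part C leaves unevaluable regions out of the region analysis.

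**4. Size.** The plan has no PPV figure to reproduce. The counts below are assumptions. With x true positives among n evaluable PET-positive cases:

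- PPV = x/n, and k moves from FP to TP give (x + k)/n, a shift of k/n.
- k moves from FP to unevaluable give x/(n − k).
- Wilson limits = [p + z²/2n ± z√(p(1 − p)/n + z²/4n²)] / (1 + z²/n), with z = 1.96.

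For 170/200, the centre is 0.8596/1.0192 = 0.8434 and the half-width is 0.0504/1.0192 = 0.0495, giving 79.4–89.3%.

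| Assumed base | Change | PPV (Wilson 95%) |
|---|---|---|
| 170/200 = 85.0% (79.4–89.3%) | 5 FP to TP | 175/200 = 87.5% (82.2–91.4%) |
| | 10 FP to TP | 180/200 = 90.0% (85.1–93.4%) |
| | 10 FP to unevaluable | 170/190 = 89.5% (84.3–93.1%) |
| | 5 TP to FP | 165/200 = 82.5% (76.6–87.1%) |
| 80/100 = 80.0% (71.1–86.7%) | 5 FP to TP | 85/100 = 85.0% (76.7–90.7%) |
| | 10 FP to TP | 90/100 = 90.0% (82.6–94.5%) |
| | 5 FP to unevaluable | 80/95 = 84.2% (75.6–90.2%) |
| | 5 TP to FP | 75/100 = 75.0% (65.7–82.5%) |

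The base of 170/200 leaves 200 − 170 = 30 false positives, so ten moves change 10/30, or one third of them, all in one direction. Eight moves give 178/200 = 89.0%, still inside the base interval. Ten clear its upper limit by 90.0 − 89.3 = 0.7 points.

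**5. Whether the written criteria give one answer.** Not always. For targeted treatment without systemic treatment, part A allows these overlaps:

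- *Visceral and prostate lesions.* A PSA fall above 50% makes the lesion TP. Growth above 20% (at least 3 mm) makes the same lesion FP.
- *Lymph nodes.* Shrinkage above 30% (at least 3 mm) makes the node TP. The absence of a PSA fall above 50% makes the same node FP.

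A criteria-only PPV cannot be computed for such lesions until the passages are reconciled.

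**The case against.** The strongest reply is that the clause is there to fill gaps. It is introduced by the remark that not every finding can be detailed, and the recording sentence speaks of interpretations that the protocol does not describe. Pathology takes priority, departures are recorded and each blinded reader is reported separately. PPV is a secondary endpoint with no hypothesis test or decision threshold. The primary endpoint (management change) and its sample size do not rest on it. Some clinical judgement is reasonable.

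Much of this stands and limits the weight of the point. It does not close the gap. The permission is worded as deviating from criteria, which is loose enough to include a covered case. Pathology priority sits under the same clause. Recording commits no one to reporting the difference.

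A reader might go further and infer that the PPV will be inflated, that every lesion threshold is open to override, or that the planned PPV necessarily includes overrides. The documents support none of these. Deviations can go either way and nothing shows selective use. The lesion criteria precede the clause. Section 1.1.9.5 is silent on which classification is used, so inclusion of overrides is possible but not stated.

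**Conclusion.** The point holds in limited form. The plan permits case-by-case departure from at least the region and patient definitions, states no blinding for that decision, and leaves open which classification the PPV uses. The size is unknown because it depends on an evaluable number, a base PPV and a deviation rate that the documents do not give. Under the assumed counts, moving 2.5% of cases from FP to TP (5 of 200) shifts the PPV by 2.5 points, and moving 5% (10 of 200) shifts it by 5 points. Only the larger shift takes the estimate outside the original interval. This is a correction worth making to a secondary endpoint and leaves the primary analysis untouched.

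**What to change.** 1. **Section 1.1.9.5.** Make the PPV under the written criteria the main reported result. Treat cases that meet neither TP nor FP criteria as unevaluable, as part A already provides, and report their number, since dropping them can itself shift the PPV. Part A ties this status to the primary endpoint; the wording should refer to PPV.
2. **Section 1.1.9.5.** Add the PPV with investigator deviations as a sensitivity analysis, with the number, direction and reason of the deviations.
3. **Section 1.1.8.4, part 2C.** Require the criteria-based result to be recorded beside every deviation, including overrides of a described criterion.
4. **Section 1.1.8.4, part 2A.** Before analysis, reconcile the overlapping TP and FP criteria for lymph node, visceral and prostate lesions so that each lesion has one classification. Failing that, report the PPV with doubly classified lesions counted each way.

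The cost is a small change to data capture, one additional analysis and the work of reconciling the criteria. No new patients or scans are needed, and investigators keep their judgement because deviations are still reported.

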#### 1) Patient level evaluation:

- a) *True positive patient*: A single region in a patient contains a true positive node either by pathology or imaging/clinical follow-up.
  - i) For a patient to be considered a True Positive, only one region is required to have a true positive lesion as described above, unless one region is categorized as a false positive based on pathology. This means that a single pathology false positive region outweighs regions with imaging/clinical follow-up true positive disease.
  - ii) A patient will be considered a True Positive if one region contains a lesion that is True Positive, even if other regions are categorized as inevaluable or false positive based on imaging or clinical follow-up.

- b) *True negative patient*: in the absence of True Positive or False Positive lesions, a patient will be considered a True Negative if there is pathology that is negative for disease and corresponding lesion is negative by F-DCFPyL PET.
- c) False positive patient:
  - i) Pathology confirms a false positive lesion that is read as positive on F-DCFPyL PET.
  - ii) In the absence of pathology: there are no true positive regions, and there is a region that is categorized as false positive based on imaging or clinical follow-up.
- d) False negative patient: in the absence of True Positive or False Positive lesions, a patient will be considered a False Negative if there is pathology that is positive for disease and corresponding lesion is negative by F-DCFPyL PET.
- 2) Region level evaluation: Each patient will have four evaluable regions (Table 1: prostate bed, pelvis, extrapelvic soft tissue, and bone metastases). Each region will be categorized as true positive or false positive as described above. Regions without evidence of F-DCFPyL positive disease or deemed unevaluable will not be included in the analysis.
  - a) True positive region:
    - i) Pathology confirms a F-DCFPyL avid lesion as a true positive in the region. ii) In the absence of pathology, clinical or imaging follow-up demonstrates a true positive lesion within the region independent of the presence of an inevaluable lesion or a false positive lesion (ie true positive disease will supersede a false positive lesion in the region based analysis if based on imaging/clinical follow-up).
  - b) *True negative region*: in the absence of True Positive or False Positive lesions within a region, the region will be considered a True Negative if there is pathology that is negative for disease in the region and corresponding lesion is negative by F-DCFPyL PET.
  - c) False positive region:
    - i) Pathology confirms a F-DCFPyL avid lesion as a false positive in the region
    - ii) In the absence of pathology, there are no true positive lesions in the region, and there is a false positive lesion by clinical or imaging follow-up.
  - d) False negative region: in the absence of True Positive or False Positive lesions in a region, the region will be considered a False Negative if there is pathology that is positive for disease in the region and corresponding lesion is negative by F-DCFPyL PET.

# 1.1.9 STATISTICAL CONSIDERATIONS

#### 1.1.9.1 Randomization

No randomization will be done.

# 1.1.9.2 Analysis Population

Endpoints will be analyzed for the entire patient cohort and for treatment groups separately (Initial and subsequent).

#### 1.1.9.3 Impact on Management Analysis Plan:

The impact of F-DCFPyL PET on clinical management patients will be evaluated using descriptive statistics for both the treatment modality analysis and the disease stage based management analysis.

# 1.1.9.4 Prognostic Value Analysis:

Clinical outcome is defined by:

- Radiographic PFS: time from inclusion to date until first site of disease is found to progress or death (whichever occurs first)
- Nodal and visceral disease is evaluated on cross-sectional imaging using RECIST 1.1/PCWG3 criteria
- b) Bone metastases are evaluated using bone scintigraphy and new lesions have to be confirmed on a second scan (2+2 rule) using PCWG3 criteria
  - Biochemical PFS: time from inclusion to date until PSA progression or death (whichever occurs first) (Scher et al., 2016)
- a) for patients with PSA decline: Time from baseline to time the PSA increase to 25% and 2 ng/ml above nadir which is confirmed by a second value ≥3 weeks later
- b) for patients without PSA decline: Time from baseline to time the PSA increase to 25% and 2 ng/ml above baseline
  - Overall survival: Time from inclusion to date of death.

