# 1.1.4 INCLUSION EXCLUSION CRITERIA

#### Inclusion criteria

- 1. Patients who fulfill criteria for initial staging or restaging as outlined below:
- 1) Initial treatment strategy decisions (initial staging)

All patients with histologically proven prostate cancer or strong suspicion of prostate adenocarcinoma based on very high PSA levels (>50 ng/mL) who require an initial treatment/management decision who may be candidate for any of the following strategies:

- A) Surgery
- B) External radiation therapy (RT) C) Other focal therapies
- D) Systemic medical treatment E)

Watchful waiting

- 2) Assessment for Subsequent treatment strategy (restaging), any of the following:
  - A) Patients with biochemical recurrence who are potential candidates for any salvage treatment. Biochemical recurrence is defined by rising PSA after definitive therapy with prostatectomy or radiation therapy, as any of the following:
    - a. Post radical prostatectomy (RP): PSA equals to or greater than 0.2 ng/mL measured more than 6 weeks after RP
    - b. Post-radiation therapy: Nadir + greater than or equal to 2 ng/mL rise in PSA
  - B) Patients with known prostate cancer who undergo restaging because of new symptoms
  - C) Patients with known metastatic prostate cancer who undergo restaging because of rising PSA with negative or inconclusive conventional imaging
  - D) Patients with known prostate cancer who are treated medically or with RLT in whom response to treatment is assessed
- 2. Capability to provide written informed consent
- 3. Able to remain still for duration of each imaging procedure (about 30 minutes)
  - \* Patients may be reenrolled in the study, if F-DCFPyL PET/CT is performed for subsequent management decision.

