## 1.1.8 ANALYSIS SPECIFICS

# 1.1.8.1 Impact on Management Questionnaires to Referring Physicians

A pre-scan questionnaire (Q1), a post-scan questionnaire (Q2) and a follow-up questionnaire (Q3) will be used to determine whether F-DCFPyL PET/CT affected intended patient management and whether these intended treatment strategies were finally implemented. Patients can only be enrolled in the study if the pre-PET questionnaire (Q1) is completed.

The post-test questionnaire (Q2), has to be completed by the referring physician within 4 weeks after each F-DCFPyL PET/CT. The final third late follow-up questionnaire (Q3), has to be completed by the referring physician within 3 to 6 months after each F-DCFPyL PET/CT. Verification of management changes will also be done via chart review and telephone interview.

Treatment Modalities and sub-modalities will be categorized as following for modality based analysis:

- A) Surgery
- a. Prostatectomy or Prostate Bed Surgery
- b. Pelvic Lymph Node dissection
- c. Solitary LN dissection
- d. Other
- B) External radiation therapy (RT)
  - a. Prostate or Prostate Bed RT
  - b. Pelvic lymph node RT
  - c. Solitary LN Stereotactic body radiation therapy (SBRT)
  - d. Lumbo-aortic RT (standard or SBRT)
  - e. Oligo-metastasis SBRT C) Other focal therapies
  - a. HIFU
  - b. Brachytherapy

- c. Cryotherapy
- d. Other
- D) Systemic medical treatment
  - a. ADT
  - b. Chemotherapy
  - c. Immunotherapy *E*) Radionuclide therapy
  - a. bone targeted radionuclide therapy
  - b. PSMA targeted radionuclide therapy F) Watchful

waiting

Treatment management will also be categorized as follow for disease stage management based analysis:

A) Local Prostate Fossa therapy B)

Regional Pelvic therapy

- C) Lombo-aortic LN focused therapy
- D) Solitary LN or oligometastatic disease focused therapy
- E) Metastatic disease systemic therapy

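### For initial-staging patients treated by prostatectomy, biochemical PFS counts no PSA event below 2.0 ng/mL, although the protocol's own definition of recurrence after that operation starts at 0.2 ng/mL

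*Combined protocol and SAP*

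**What the plan says.** The first secondary endpoint (1.1.3.3) is the prognostic value of the "miTNM classification (described below) for biochemical PFS, radiographic PFS and overall survival". Section 1.1.9.4 defines biochemical PFS as running from inclusion to PSA progression or death. PSA progression has two branches:

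- (a) "for patients with PSA decline: Time from baseline to time the PSA increase to 25% and 2 ng/ml above nadir"; here a repeat measurement, taken three weeks afterwards at the earliest, must bear the rise out;
- (b) for patients whose PSA does not decline, the same two margins above baseline, with no confirmation stated.

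No branch depends on the treatment given. Section 1.1.9.2 applies the endpoints to the whole cohort and to the initial and subsequent groups separately.

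Section 1.1.4 defines biochemical recurrence for entry to the restaging group by prior treatment. After prostatectomy it is "PSA equals to or greater than 0.2 ng/mL measured more than 6 weeks after RP". After radiation it is "Nadir + greater than or equal to 2 ng/mL rise in PSA". Surgery is among the options for initial-staging patients in 1.1.4, and "Prostatectomy or Prostate Bed Surgery" is a coded treatment in 1.1.8.1. Re-enrolment is allowed when a further scan serves a subsequent management decision.

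**The concern.** The protocol recognises that a PSA of 0.2 ng/mL after prostatectomy signals recurrence, yet its biochemical outcome cannot register that recurrence until PSA is at least ten times higher. An initial-staging patient who has surgery can later meet the 1.1.4 recurrence definition, and be re-enrolled for restaging if he is a salvage candidate, while his first record still shows no PSA event.

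What is at stake is the number and timing of events in the miTNM prognostic analysis for this subgroup. Recurrences between 0.2 and 2.0 ng/mL are dated late. Some may be missed altogether, because 1.1.4 enrols recurrent patients as potential candidates for salvage treatment, and effective treatment can lower PSA before it reaches the event level. Splitting the analysis into initial and subsequent groups does not help, since the same rule applies within the initial group.

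The protocol gives no reason for using one rule in every setting. The source cited for it is, by its title in the reference list, a set of trial-design recommendations for castration-resistant disease, whereas the initial-staging group consists of men facing a first treatment decision.

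**Working it through.** The plan states no figure to reproduce here, so the check is of the threshold itself.

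**Lowest PSA that can be an event.** Let R be the reference value: nadir in branch (a), baseline in branch (b). Both margins in 1.1.9.4 are required, so

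event level = max(1.25 × R, R + 2).

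The two terms are equal at R = 8 ng/mL (1.25 × 8 = 8 + 2 = 10). Below 8 the absolute margin of 2 ng/mL decides. PSA cannot be negative, so the minimum under either branch is 0 + 2 = 2.0 ng/mL.

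For low nadirs after surgery (assumed values; the documents give none):

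| Nadir (ng/mL) | Event level (ng/mL) | Ratio to 0.2 |
|---|---|---|
| 0 | 2.00 | 10.0 |
| 0.05 | 2.05 | 10.25 |
| 0.1 | 2.10 | 10.5 |
| 0.2 | 2.20 | 11.0 |

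A patient with nadir 0.05 who rises to 0.2 meets the 1.1.4 definition, but has no PSA event until 2.05.

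**Comparison with 1.1.4 by treatment.**

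- After radiation, 1.1.4 uses nadir + 2. For nadirs up to 8 ng/mL this is the same level as in 1.1.9.4, so the two sections agree.
- After prostatectomy, 1.1.4 uses an absolute 0.2 ng/mL. Only this case is out of step.

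**Illustrative delay.** For an untreated exponential rise, delay = doubling time × log2(event level / 0.2). The doubling times are assumptions; the documents state none.

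- To 2.0: log2(10) = 3.32 doublings. At 3, 6 and 12 months this is 10.0, 19.9 and 39.9 months.
- To 2.2: log2(11) = 3.46 doublings. The same doubling times give 10.4, 20.8 and 41.5 months.

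These figures show the scale of the gap for one patient. They do not estimate how many patients are affected.

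**The case against.** The strongest reply is that the two sections define different things. Section 1.1.4 sets who may enter; 1.1.9.4 defines an outcome and cites a source for it. Nothing requires the thresholds to match, and one rule keeps events comparable across a mixed cohort that is also analysed as a whole. This stands in part: a reader who inferred a formal contradiction would be wrong, and the common rule deserves to stay. But comparability does not explain why an operated patient's recurrence, by the protocol's own definition, should go uncounted in the only biochemical outcome.

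Death still counts as a biochemical PFS event, and radiographic PFS and overall survival are separate outcomes. That is true, but biochemical PFS is named in its own right, and it is the PSA component that is lost.

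It is also fair that other gaps in 1.1.9.4 are wider: it gives no model, no miTNM grouping and no censoring rule. That affects the order of work, not whether this point holds.

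A reader might set the delays against study completion at 48 months and work out which doubling times could produce an event in time. The documents do not support such limits. They set no PSA schedule after the scan, an untreated rise sits poorly with patients being salvage candidates, and month 36 is primary completion, not a stated end of accrual (400 patients at 100 per year is 48 months).

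**Conclusion.** The point holds for initial-staging patients whose implemented treatment is prostatectomy. For them no PSA value below 2.0 ng/mL can be an event under either branch, a level at least ten times the protocol's own post-prostatectomy recurrence threshold. Recurrences in between are dated late, or missed if treatment lowers PSA first, so the miTNM analysis loses biochemical events in this subgroup.

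Two wider readings are not supported. One is that the problem covers every post-prostatectomy patient: those enrolled for recurrence after surgery already have PSA of at least 0.2 at entry, so that threshold cannot serve as their outcome. The other is that the miTNM association is biased: a higher threshold delays events at every stage, and nothing in the documents shows that it does so unequally.

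The threshold result rests only on reading the two margins as jointly required, which is what the text says. The delays rest on assumed doubling times and an untreated rise. The size of the subgroup and the share of recurrences affected cannot be derived. The primary endpoint and the sample size of 400 are unaffected. The change is worth making, at secondary-endpoint priority.

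**What to change.** Keep the 1.1.9.4 rule for the whole-cohort and group analyses. Add to that section one prespecified supplementary biochemical PFS analysis:

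- **Population:** initial-staging patients whose implemented treatment, established as in 1.1.8.4, is prostatectomy. Patients enrolled for recurrence after prostatectomy are excluded.
- **Event:** the 1.1.4 definition (PSA of 0.2 ng/mL or above, later than 6 weeks from the operation) or death. Section 1.1.4 asks for no confirmatory value; the new text should say whether that carries over.
- **Time origin:** surgery, not inclusion. Patients must survive to surgery and cannot have a PSA event until 6 weeks after it, so timing from inclusion would build in event-free time.
- **PSA that never falls below 0.2:** an event at the first value later than 6 weeks from surgery. This needs stating because 1.1.4 speaks of a rising PSA.

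The cost is a few sentences, one extra derivation and one extra analysis. Surgery dates and PSA values would have to come from chart review, and with no set PSA schedule the event dates will be only as precise as routine testing allows. The subgroup is defined by treatment chosen after the scan, which the scan may have influenced, and its miTNM range may be narrow. The result should therefore be labelled supplementary, read on its own, and not compared with other treatment groups.
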